8.10.2.1 Secondary Efficacy Analyses at Secondary Endpoints

Crossover Subject Analyses

LSAS data from subjects assigned to the placebo group, i.e. ‘crossover population,’ will be analyzed by t-tests on difference scores from Stage 1 endpoint (Visit 13) to Stage 2 endpoint (Visit 22) only if there is sufficient data to examine.

6-month Follow-up Analyses

To determine durability of effects, LSAS data will be analyzed by t-tests on difference scores from Stage 1 endpoint (Visit 13) to 6-month follow-up. Additionally, the following measures’ scores will be analyzed in this same fashion: PSS, BDI-II, IRI, RSES, STAI, TASIT, TAS-20, ERQ, QoL-Q

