4.0 Protocol Design

Twelve subjects meeting eligibility criteria will be enrolled. Throughout the study, the study therapists will maintain communication with the referring physician or therapist and any other health care providers requested by the subject. In consultation with their prescribing physician, any individuals taking psychiatric medications will taper off these medications, allowing for a washout period of at least 5 times the medication and active metabolite half-lives plus one week for stabilization before the experimental session. During the study, benzodiazepines or atypical antipsychotics may be used to alleviate severe distress or panic responses if other interventions are ineffective. Subjects who are in psychotherapy with an outside therapist at the time of enrollment may continue that therapy during the treatment period without increasing the number or type of sessions or changing type of psychotherapy until after the outcome assessment, one month after the second experimental session in Stage 1. After the treatment period, subjects may resume psychotropic medications and may change therapists or psychotherapy type.

Each of the 12 subjects will participate in two experimental MDMA-assisted therapy sessions of seven hours in duration within a brief course of non-drug therapy, including three preparatory sessions at the start of the study and three integrative sessions during the month after each experimental session. During preparatory sessions, subjects will learn what to expect during experimental sessions and complete pre-treatment assessments. The second preparatory session will include a comprehensive tour of the treatment location and introductions to all available research and support personnel who subjects are likely to see during experimental sessions. In-person visits will occur in a private room in an outpatient research facility. All in-person sessions after enrollment may be video recorded for the purposes of evaluating structural elements of therapy for effectiveness and feasibility. Video recordings will be used for research and training purposes during and after the study.

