4.1 Planned Duration of Study

- Subjects in Stage 1 and follow-up: 8 months
- Subjects in Stage 1, follow-up, and Stage 2: 10 months

These lengths of time do not include screening, which may take up to two months. The total duration of the study will depend on enrollment rates, but is expected to last at least 22 months. Any delay between visits would result in a corresponding extension of study duration.

Table 2. Time & Events Stage 1

Study Phase	Baseline		Preparatory Sessions			Experimental Session	Integrative Sessions			Experimental Session	Integrative Sessions			Follow-up	6-Month Follow-up
	V1	V2	V3	V4	V5	V6	V7	V8	V9	V10	V11	V12	V13	(remote)	V14
Visit Timing			Week 1	Week 2	Week 3		1 day later	2 Wks later	2 Wks later	Apr. 1 Month after V6	1 day later	2 Wks later	2 Wks later	Monthly By Mail	6 Months after V10
Informed Consent	✓														
Medical/Psychiatric History & Evaluation	✓														
SCID	✓														
General Physical Exam (includes neurological)		✓													
Screening Clinical Lab Tests, EKG		✓													
ADOS-2		✓ ^H													
LSAS		✓ ^{G,H}					✓ ^G	✓ ^G	✓ ^G		✓ ^G	✓ ^G	✓ ^G		✓ ^G
C-SSRS		✓			✓	✓ ^{A,C,D}	✓ ^E	✓	✓	✓ ^{A,C,D}	✓ ^E	✓	✓		✓
Feedback Questionnaire, Qualitative Interview		✓													✓
Study Enrollment if Eligible			✓												
Collect Concomitant Medication	✓		✓	✓	✓	✓	✓	✓	✓	✓	✓	✓	✓		✓
Start Medication Taper (if applicable)			✓												✓ ^I
Collect Serology Samples (OT, AVP, CORT)		✓								✓			✓		✓
Record to Video			✓	✓	✓	✓	✓	✓	✓	✓	✓	✓	✓		✓
General Wellbeing			✓	✓	✓	✓	✓	✓	✓	✓	✓	✓	✓		✓
Pregnancy Screen (if applicable), Drug Screen		✓				✓				✓					
BDI-II, STAI			✓				✓	✓	✓		✓	✓	✓	✓	✓
PSS			✓				✓				✓		✓	✓	✓
IRI, RSES			✓				✓				✓		✓		✓
TASIT				✓		✓				✓			✓		✓
ERQ, TAS-20					✓								✓		✓
QoL-Q					✓										✓
Administer Drug + Therapy						✓				✓					
Monitoring of BP, Pulse, and Temperature, SUD						✓ ^{A,B,C}				✓ ^{A,B,C}					
Belief of Condition Assignment							✓				✓				
Integrative Therapy Session							✓	✓	✓		✓	✓	✓		
Start 7 Days Phone Contact							✓				✓				
Spont. Reported Reactions & All Adverse Events						✓	✓ ^F	✓		✓	✓ ^F	✓			
Symptoms at Baseline	✓		✓	✓	✓	✓	✓	✓	✓	✓	✓	✓	✓		✓
Adverse Events Requiring Doctor's Visit			✓	✓	✓	✓	✓	✓	✓	✓	✓	✓	✓		✓
Adverse Events Causing Withdrawal, SAEs			✓	✓	✓	✓	✓	✓	✓	✓	✓	✓	✓	✓	✓
Unblinding & Termination															✓ ^J
Approximate Hours for Study Visit	3	1.8	1.5	1.5	1.8	8.0	1.9	1.7	2.1	8.0	1.9	1.7	2.6	0	2.2

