- l. Assess status of symptoms at baseline specific to the study population.
- m. Remind the subject that the last integrative session in Stage 1 that this will be the last in-person visit prior to the 6-month Follow-up visit, and that some measures will be collected monthly by mail.
- n. Review how to use the Memory Aid Card with the subject. Subjects will use this card to record AEs, medications, and changes in psychiatric status that they will be asked about at the 6-month follow-up visit. Memory Aids will not be collected.

5.2.7 6-Month Follow-up

Subjects who have withdrawn from treatment but have continued for follow-up will also complete these assessments whenever possible. During the follow-up period:

- a. Subjects may return to taking psychiatric medications or change frequency or method of psychotherapy received from outside therapists if necessary.
- b. The following self-report measures will be completed by subjects and collected monthly at two, three, four, and five months after the second experimental session by mail:
 - a. BDI-II
 - b. STAI
 - c. PSS
- c. At the 6-month follow-up, an in-person visit will be conducted.
- d. The IR will administer the LSAS.
- e. Collect information on phase of menstrual cycle for female subjects.
- f. Blood will be drawn for biomarker analysis.
- g. Subjects will complete self-report outcome assessments, including:
 - a. ERQ
 - b. TAS-20
 - c. TASIT
 - d. QoL-Q
 - e. RSES
 - f. IRI
 - g. BDI-II
 - h. STAI
 - i. PSS
 - j. Feedback Questionnaire
- h. Review specified AEs and medications as described in Section 8.5 and Section 9.0. Subjects should bring the Memory Aid Cards to this visit, to be used as aids in recollection. These cards will not be collected.
- i. Assess status of symptoms at baseline specific to the study population.
- j. One of the therapists will assess suicidality with the C-SSRS.
- k. General wellbeing will be assessed.
- l. The therapists will review the responses to the Feedback Questionnaire assessing effects of the study with the subject. During the qualitative interview, additional follow-on questions may be asked to elucidate self-reported responses on the questionnaire.
- m. After all assessments are complete, the therapists will break the blind for the individual subject.
- n. Subjects who were randomized to the MDMA group will complete the termination visit at this time.

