2.0 Introduction

This document presents a Statistical Analysis Plan (SAP) for MAPS study protocol MAA-1, a Phase 2 pilot clinical trial designed to evaluate the safety, feasibility, and efficacy of MDMA-assisted psychotherapy in treating social anxiety in adults on the autism spectrum.

The Multidisciplinary Association for Psychedelic Studies (MAPS) is a non-profit research and educational organization working to obtain approval for the prescription use of 3,4-methylenedioxymethamphetamine (MDMA)-assisted psychotherapy in adults on the autism spectrum with social anxiety. This is an initial pilot study to assess the efficacy of MDMA for this indication, following promising results from MAPS-sponsored studies of MDMA-assisted psychotherapy for posttraumatic stress disorder (PTSD).

The Phase 2 pilot study will examine the safety, feasibility, and efficacy of MDMA-assisted psychotherapy for social anxiety in 12 MDMA-naïve adults on the autism spectrum. This study is designed as a dose escalation study to assist with the exploration of safety and finding the most effective dose in this population. Subjects assigned to the MDMA group will receive two of three different doses, either 75 mg, 100 mg, or 125 mg MDMA. Overall, eight subjects (66.7%) will be randomized to the MDMA group and four subjects (33.3%) will be randomized to the placebo group. Subjects who received the placebo during Stage 1 will have the opportunity to cross over and take part in a second study segment, referred to as Stage 2, with two open-label experimental sessions, after completing the six-month follow-up visit at the end of Stage 1.

This study is designed to obtain safety data, and secondarily estimates of effect size for efficacy. The data will be used to determine study design and dosing for future studies for this indication. MAA-1 is also intended to contribute to the development of a manualized psychotherapeutic approach to this potential treatment. This study is exploratory. As a result, the sponsor will perform tests on all statistical comparisons without correcting for multiple comparisons.

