3.2 Secondary Objectives

The following objectives will compare MDMA and placebo groups in the blinded Stage 1:

- To assess effects on levels of oxytocin (OT), arginine vasopressin (AVP), and cortisol (CORT) in peripheral blood at baseline, once during each experimental session between hours 2 – 3, one month after the second experimental session, and at 6-month follow-up.
- To assess effects on social perception using The Awareness of Social Inference Test (TASIT) at baseline, once during each experimental session between hours 2-3, one month after the second experimental session, and at 6-month follow-up.

- To assess effects on emotion labeling using the Toronto Alexithymia Scale-20 (TAS-20) at baseline, one month after each experimental session, and 6-month follow-up.
- To assess effects on emotion regulation using the Emotion Regulation Questionnaire (ERQ) at baseline, one month after each experimental session, and 6-month follow-up.
- To assess effects on depression symptoms as measured by the Beck Depression Inventory-II (BDI-II) at baseline, one day, two weeks, one month after each experimental session, monthly by mail during the 5 months leading up to the 6-month follow-up assessment.
- To assess effects on perceptions of stress as measured by the Perceived Stress Scale (PSS) at baseline, within 24 hours after each experimental session, one month after each experimental session and monthly by mail leading up to the 6-month follow-up assessment.
- To assess effects on four aspects of empathy, as measured by the Interpersonal Reactivity Index (IRI) at baseline, within 24 hours after each experimental session, one month after each experimental session, and at the 6-month follow-up assessment.
- To assess effects on self-esteem as measured by the Rosenberg Self-Esteem Scale (RSES) at baseline, within 24 hours after each experimental session, one month after each experimental session, and at the 6-month follow-up assessment.
- To assess effects on state and trait anxiety as measured by the State-Trait Anxiety Index (STAI Form Y) at baseline, one day, two weeks, and one month after each experimental session, and monthly by mail leading up to the 6-month followup assessment.

The following objectives will compare effects in specified subjects:

- To determine if subjects who receive placebo in Stage 1 show a reduction in LSAS scores after two open-label sessions in the Stage 2 crossover

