4.0 Study Design

This randomized, double-blind, placebo-controlled study will examine the safety, feasibility, efficacy of MDMA-assisted psychotherapy in twelve adults on the autism spectrum with social anxiety. Each of the 12 subjects will participate in two experimental drug-assisted (MDMA or placebo) therapy sessions of seven hours in duration within a brief course of non-drug therapy, including three preparatory sessions at the start of the study and three integrative sessions during the month after each experimental session.

Upon enrollment, the first six subjects (Group 1) will be randomized to receive one dose of either placebo (N=2) or 75 mg MDMA (N=4). In the second experimental session one month later, Group 1 subjects randomized to MDMA will escalate to 100 mg MDMA, unless contraindicated by safety and tolerability concerns. The second six subjects (Group 2) will be randomized to receive one dose of either placebo (N=2) or 100 mg MDMA (N=4). In the second experimental session one month later, Group 2 subjects randomized to MDMA will escalate to 125 mg MDMA, unless contraindicated by safety and tolerability concerns. Subjects randomized to placebo in Group 1 and Group 2 will receive placebo in both experimental sessions also scheduled one month apart. The blind will be maintained through the six-month follow-up for each individual subject, after which the blind will be broken. Placebo subjects will be offered an open-label extension (Stage 2) with two experimental sessions scheduled one month apart, in addition to three hour-long integrative sessions during the month after each experimental session. Stage 2 subjects will receive 75 mg MDMA in the first experimental session and will escalate to 125mg MDMA in the second experimental session, unless contraindicated by safety and tolerability concerns from other subjects in Stage 1. Subjects will attend a 1-hour follow-up integrative therapy session on the day after the experimental session. Two additional integrative sessions will be conducted within the month following each experimental session, prior to outcome assessments being conducted one month after each experimental session.

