8.10.1 Primary Efficacy Analyses

Liebowitz Social Anxiety Scale (LSAS)

The primary efficacy evaluation is the change from baseline to the primary outcome timepoint (visit 13, one month post experimental session 2) in the LSAS score of Social Anxiety (difference score). The primary efficacy comparison on difference scores will be made with independent sample t-tests at an alpha level of 0.05. If the primary hypothesis rejects, pairwise comparisons among the treatment groups will be made with t-tests. If the parametric assumptions for the t-test analyses are not met, the analogous nonparametric methods will be used (Wilcoxon Rank Sum Test). If data has normal distribution, Cohen's d placebo-subtracted effect size will be estimated on mean difference scores from baseline to Visit 13 with confidence intervals.

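### The only planned Stage 2 crossover test runs from V13 to V22, so it includes about five months before open-label MDMA and does not isolate the change that SAP 3.2 asks about; add V14-to-V22 beside it.

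*SAP*

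**What the plan says.** SAP 3.2 sets the crossover objective: to determine whether placebo subjects "show a reduction in LSAS scores after two open-label sessions in the Stage 2 crossover". Protocol 3.2 words its own version differently, as a within-subject comparison of Stage 1 LSAS outcomes with Stage 2 open-label outcomes.

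SAP 8.10.2.1 gives one analysis for this: t-tests on LSAS "difference scores from Stage 1 endpoint (Visit 13) to Stage 2 endpoint (Visit 22", to be run only if there are enough data. The next paragraph of that section separately tests V13 to 6-month follow-up as durability of effect.

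The timing is set out in several places:

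- SAP 8.10.1 defines the Stage 1 endpoint as "visit 13, one month post experimental session 2".
- Protocol Table 2 places V14 at "6 Months after V10", V10 being the second blinded session.
- SAP 2.0 lets placebo subjects cross over "after completing the six-month follow-up visit at the end of Stage 1".
- SAP 4.0 says: "The blind will be maintained through the six-month follow-up for each individual subject, after which the blind will be broken".

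The restrictions on other treatment are relaxed in the gap. Protocol 4.0 says: "After the treatment period, subjects may resume psychotropic medications and may change therapists or psychotherapy type". Protocol 5.2.7 says of the follow-up period: "Subjects may return to taking psychiatric medications or change frequency or method of psychotherapy received from outside therapists if necessary". Protocol 9.0 then requires subjects to be without psychiatric medication during treatment in both Stage 1 and Stage 2. Table 2 marks a taper start at V14 for Stage 2 subjects, and Table 3 marks its end before V15.

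**The concern.** The SAP objective concerns change after the open-label sessions, but the planned difference score starts well before those sessions can take place. Whatever happens to social anxiety between V13 and the start of Stage 2 is counted with whatever happens afterwards. Crossover subjects have no concurrent control group, so nothing cancels that first part. Improvement during follow-up would be credited to open-label MDMA, and worsening during follow-up could hide a response to it.

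This matters because the trial exists to supply effect estimates for sizing later studies (SAP 2.0 and 6.0), and this is its planned test of response to open-label MDMA in subjects first given placebo. A better-placed starting score is already collected. The independent rater gives the LSAS at V14, before the blind is broken, and Table 3 schedules none at V15, so V14 is the last score before open-label dosing.

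**Working it through.** **1. Timeline, checked against the stated durations.** Inputs: Protocol Tables 1, 2 and 3 and section 4.1.

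- V10 (second blinded session): Month 2.
- V13 = V10 + 1 day + 2 weeks + 2 weeks = V10 + 29 days, about Month 3.
- V14 = V10 + 6 months = Month 8. Section 4.1 states 8 months for Stage 1 and follow-up: reproduced.
- V22 = V14 + about 2 months = Month 10. Section 4.1 states 10 months with Stage 2: reproduced.

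**2. Share of the contrast that precedes Stage 2.**

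- V13 to V14: 8 − 3 = 5 months. In days, 6 × 30.44 − 29 ≈ 154, or 5.0 months.
- V13 to V22: 10 − 3 = 7 months.
- Share before Stage 2: 5/7 = 71%.

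Table 1 in both documents instead labels the first Stage 2 session Month 6 and the second Month 7. That would put V22 near Month 8, with 6 − 3 = 3 of 8 − 3 = 5 months before treatment (60%). The label conflicts with V14 at Month 8. SAP 4.0 also places a 6-month follow-up after Stage 1 or Stage 2, while Protocol 5.2.8 gives Stage 2 subjects no additional one. These passages need reconciling. On either timeline a large part of the contrast is pre-treatment.

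**3. Decomposition.** For each subject,

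(V22 − V13) = (V14 − V13) + (V22 − V14).

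Only the second term can contain the effect of the open-label sessions. A persisting mean shift of *d* points in the first term, from spontaneous change or changed psychotherapy, moves the V13-to-V22 estimate by *d*.

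**4. Restarted drugs behave differently.** Subjects are to be off psychiatric drugs at V13 and at V22. Suppose, as an illustration, that a drug restarted after V13 lowers the LSAS by 10 points at V14 and that this reverses on taper.

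- Bias in V22 − V13: 0 points.
- Bias in V22 − V14: +10 points, which would mask a response.

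So this pathway mainly affects V14. Only a lasting benefit or a taper effect would remain in V13-to-V22.

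**5. Illustrative false-significance rates.** The documents give neither an SD for the change nor a drift, so both are assumed. Take no Stage 2 effect, a paired t-test (two-sided 0.05), n = 4, 3 degrees of freedom, critical value 3.182, and noncentrality = drift/(SD/√4).

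| Mean drift (points) | SD 15 | SD 10 |
|---|---|---|
| 5 | 7.7% | 11.1% |
| 10 | 15.9% | 28.9% |
| 20 | 44.9% | 75.5% |

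With n = 3 and SD 15 the rates are 6.5%, 11.0% and 26.8%. The nominal rate is 5%. The bottom row needs a common mean drift of 20/15 = 1.3 SD or 20/10 = 2 SD, which is large. Changes affecting only some subjects could instead mainly widen the spread.

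**The case against.** The best defence is that V13 and V22 are matched visits. Each is the last integrative visit of its stage, about one month after that stage's second session, with psychiatric drugs withheld. Comparing them sets outcome on placebo against outcome on open-label MDMA, which is a fair reading of the objective in Protocol 3.2 and of the Stage 1 versus Stage 2 comparison in Protocol 12.0. This stands: V13-to-V22 answers a legitimate question and should be kept. It does not answer the SAP 3.2 question about reduction after the open-label sessions.

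A reader might infer that restarted medication passes in full into the V13-to-V22 estimate, or that V14 should simply replace V13. The documents support neither. The off-drug rule at both visits largely removes the drug pathway from V13-to-V22. V14 is also an imperfect baseline: it may be taken on a restarted drug, and taper and washout (up to 45 days in Protocol Table 5) can separate it from V15.

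Setting the Stage 1 change from V2 against the Stage 2 change from V14 would not be like with like either. V2 is a screening score in subjects required to have at least moderate anxiety, so regression to the mean is possible, and the Stage 1 change spans preparatory sessions that Table 3 does not schedule in Stage 2.

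The SAP also already analyses V13 to 6-month follow-up, with descriptive statistics by treatment group under 8.10, so movement over the gap will be visible in part. It is not linked to the crossover result.

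**Conclusion.** The point holds in limited form. As the only crossover analysis, V13-to-V22 does not isolate the change that SAP 3.2 asks about, because about five of its seven months (about three of five on Table 1's label) come before any open-label dose. The bias equals the mean shift over the gap that persists to V22, can run in either direction, and comes mainly from spontaneous change and changed outside psychotherapy.

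The five-month figure rests on Table 2, the rule that Stage 2 follows V14, and the 8- and 10-month durations, with no delay between visits. The rates of 8% to 45% (SD 15) and 11% to 76% (SD 10) are correct arithmetic on assumed inputs and should not be read as a forecast.

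The consequence is confined to a secondary analysis of at most four subjects, run only if data suffice, in a study declared exploratory. A reader might infer that the primary Stage 1 comparison is affected; it is not, because it uses baseline to V13 only.

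**What to change.** In SAP 8.10.2.1:

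- Add LSAS change from V14 to V22 as the analysis for the SAP 3.2 crossover objective.
- Keep V13-to-V22 as the matched, off-drug comparison of Stage 1 outcome with Stage 2 outcome (Protocol 3.2), and state which question each contrast answers.
- Present both next to the planned V13-to-6-month change for the same subjects.
- List the four or fewer crossover subjects individually at V13, V14 and V22, flagging any change in psychiatric medication or outside psychotherapy after V13.
- Reconcile Table 1's Month 6 and Month 7 labels with Table 2 and Protocol 4.1, and SAP 4.0 with Protocol 5.2.8 on follow-up after Stage 2.

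The cost is SAP wording and one small listing. The V14 LSAS is already scheduled, and Protocol 9.0 already collects psychiatric medication changes. Changes in outside psychotherapy can be flagged only as far as they are recorded. The downside is that V14 may be on-drug and is separated from V15 by any taper, so neither contrast should be read alone.

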3.0 Protocol Objectives

The main objective of this study is to collect safety data to examine whether MDMA-assisted therapy will be tolerated and to estimate effect size of symptom reduction in social anxiety that is common in the adult autistic population as evaluated by standard clinical measures.

3.1 Primary Objective:

To estimate effect sizes of social anxiety symptom reduction between MDMA and placebo, as measured by the clinician-administered LSAS administered by a blinded IR, at baseline, one day, two weeks, and one month after each experimental session, and at 6-month follow-up.

3.2 Secondary Objectives:

The following objectives will compare MDMA subjects to placebo subjects in Stage 1:

- To assess effects on levels of OT, AVP, and CORT in peripheral blood at baseline, once during each experimental session between hours 2 – 3, one month after the second experimental session, and at 6-month follow-up.
- To assess effects on social perception using The Awareness of Social Inference Test (TASIT) at baseline, once during each experimental session between hours 2 – 3, one month after the second experimental session, and at 6-month follow-up.
- To assess effects on emotion labeling using the Toronto Alexithymia Scale-20 (TAS-20) at baseline, one month after each experimental session, and 6-month follow-up.
- To assess effects on emotion regulation using the Emotion Regulation Questionnaire (ERQ) at baseline, one month after each experimental session, and 6-month follow-up.
- To assess effects on depression symptoms as measured by the Beck Depression Inventory-II (BDI-II) at baseline, one day, two weeks, one month after each

- experimental session, monthly by mail during the 5 months leading up to the 6-month follow-up assessment.
- To assess effects on perceptions of stress as measured by the Perceived Stress Scale (PSS) at baseline, within 24 hours after each experimental session, one month after each experimental session and monthly by mail leading up to the 6-month follow-up assessment.
 - To assess effects on four aspects of empathy, as measured by the Interpersonal Reactivity Index (IRI) at baseline, within 24 hours after each experimental session, one month after each experimental session, and at the 6-month follow-up assessment.

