3.0 Analysis Plan Objectives

3.1 Primary Objective

The primary objective is to assess changes in social anxiety symptoms between MDMA and placebo groups, as measured by the clinician-administered Liebowitz Social Anxiety Scale (LSAS) administered by a blinded Independent Rater (IR), at baseline, one day, two weeks, and one month after each experimental session, and at 6-month follow-up.

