5.0 Randomization and Blinding

This is a randomized, double-blind, placebo-controlled study with an open-label cross-over segment. For Stage 1, a randomization list will be prepared at the beginning of the study. If needed, subsequent randomization lists will be created to replace subjects who withdraw from the study to ensure that replacement subjects are not added to the end of the initial list. Each subject will be assigned to one of the two dose conditions: 0 mg (placebo) or 125 mg (full dose). Eight evaluable subjects will be assigned to the full dose condition, and four to the placebo condition. The study will employ a blinded randomization procedure that will maintain the 8:4 ratio while maintaining the blind and ensuring that each subsequent condition assignment is not predicated on the previous assignment.

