8.0 Analyses

In general, nominal variables will be described in terms of frequencies and percentages and analyzed using chi square analysis. Ordinal and non-normal continuous variables will be described using sample median and range, and analyzed by non-parametric statistical tests, and approximately normal variables will be described using sample mean and standard deviations and analyzed by parametric statistical tests. All statistical tests will be two-sided. All p-values will be rounded to and displayed in four decimals. If a p-value less than 0.0001 occurs it will be shown in tables as <0.0001. For any analysis that is called out as parametric, e.g. t-test, the parametric assumptions will be examined. If necessary, nonparametric analyses will be utilized, e.g. Wilcoxon rank-sum test.

Clinical data will be presented in tabular format. Data not subject to analysis according to this plan will not appear in any tables or graphs, but will be included in the data listings. Analyses will be carried out with SAS Version 9.3 or higher. Selected results may be presented graphically using standard graphical software.

Post-hoc exploratory analyses not identified in this SAP may be performed to further examine the study data. These analyses will be clearly identified as such in the final clinical study report.

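### The SAP tests 6-month durability only as LSAS change since Visit 13 and defines no MDMA-minus-placebo estimate from baseline to 6 months, although the primary objective names that visit.

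*SAP*

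**What the plan says.** The SAP's primary objective (3.1) compares MDMA and placebo on the independent-rater LSAS "at baseline, one day, two weeks, and one month after each experimental session, and at 6-month follow-up". The protocol's primary objective (3.1) covers the same visits and is worded as estimation: "To estimate effect sizes of social anxiety symptom reduction between MDMA and placebo".

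SAP 8.10.1 then fixes the primary contrast as baseline to Visit 13: "The primary efficacy comparison on difference scores will be made with independent sample t-tests at an alpha level of 0.05". Cohen's d is tied to the same interval: "effect size will be estimated on mean difference scores from baseline to Visit 13 with confidence intervals". The secondary analyses in SAP 8.10.2 also end at Visit 13.

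For the 6-month visit, SAP 8.10.2.1 says: "To determine durability of effects, LSAS data will be analyzed by t-tests on difference scores from Stage 1 endpoint (Visit 13) to 6-month follow-up". It applies the same approach to nine secondary scales, including QoL-Q. It states no margin, confidence interval or rule for reading the result, and does not say whether the t-test is within or between arms. SAP 1.0 defines difference scores as serving both kinds of comparison, so it does not settle the question.

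Other text bears on 6 months without closing the gap. SAP 8.10 plans descriptive statistics by group for all endpoints. Protocol 12.0 plans plots through six months, Cohen effect sizes for all outcome measures, and main effect-size estimates once the six-month assessments are complete. Its list of effect sizes that reach into follow-up names eight secondary scales and omits LSAS.

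**The concern.** The null hypothesis of the planned test is no change since Visit 13. Failing to reject it does not show that benefit was kept, least of all in a sample this small. Rejecting it does not answer the clinical question either: a subject group can worsen after Visit 13 and still be better off than placebo, and the test does not measure that remaining difference.

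The trial exists to supply effect sizes for later studies. A time point named in the primary objective therefore ought to have a defined treatment-effect estimate with an interval. The data for it will exist: Protocol Table 2 schedules the independent-rater LSAS at Visit 14, and the blind for each subject is broken only after that visit's assessments (Protocol 5.2.7).

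**Working it through.** The plan gives no SD, effect size, correlation, margin or power for this test, so there is no figure to reproduce. The check is how often the planned test would miss a real loss of benefit.

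**Inputs from the documents.** 8 MDMA and 4 placebo subjects (SAP 5.0). Two-sided tests ("All statistical tests will be two-sided", SAP 8.0). Alpha 0.05, stated for the primary comparison in SAP 8.10.1 and assumed to carry over.

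**Assumptions.** Equal SD at each visit, taken as 1. Visit 13 effect of 0.8, 1.0 or 1.5 SD. Correlation r between Visits 13 and 14 of 0.5, 0.7 or 0.8. All 12 subjects rated. No change after Visit 13 in the placebo arm. The within-arm figures treat the effect as the MDMA arm's own change.

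**Formulas.** Let Δ be the part of the effect lost between Visits 13 and 14.
- SD of change: s = √(2(1 − r)), which is 1.000, 0.775 and 0.632 for r = 0.5, 0.7 and 0.8.
- Within MDMA (n = 8): df = 7, critical t = 2.365, noncentrality = (Δ/s)·√8.
- Between arms (8 vs 4): df = 10, critical t = 2.228, noncentrality = (Δ/s)·√(8·4/12) = 1.633·Δ/s.
- Miss rate: the probability that |t| stays below the critical value under the noncentral t.

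**Worked case.** A 0.8 SD effect lost completely, r = 0.7: Δ/s = 0.8/0.775 = 1.033. The noncentralities are 2.92 (within) and 1.69 (between), and the miss rates are 29% and 67%. If half is lost, Δ = 0.4 and the miss rates are 76% and 88%.

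**Miss rates as r goes from 0.8 to 0.5:**

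| Visit 13 effect | Lost | Within MDMA | Between arms |
|---|---|---|---|
| 0.8 SD | half | 66–83% | 85–91% |
| 0.8 SD | all | 14–50% | 54–78% |
| 1.0 SD | all | 3–32% | 36–68% |
| 1.5 SD | half | 18–55% | 58–80% |
| 1.5 SD | all | 0–5% | 6–40% |

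**Precision of the missing estimate.** The 95% CI half-width for the between-arm difference in change is 2.228 × √(1/8 + 1/4) × s = 1.364·s. That is 1.36, 1.06 and 0.86 visit SDs at r = 0.5, 0.7 and 0.8, with r now the baseline-to-Visit-14 correlation.

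**Could a formal maintenance test be run instead?** Take one-sided 0.025, 80% power, 2:1 allocation and the normal approximation, with an assumed margin of 0.5 SD of the change. The smaller arm needs (1.960 + 0.842)² × 1.5 / 0.5² = 47.1, so 48, and 48 + 96 = 144 in total. With a 1.0 SD margin it needs 11.8, so 12, and 12 + 24 = 36. The trial has 12 subjects.

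**QoL-Q.** Protocol Table 2 schedules it only at Visits 5 and 14, and Protocol 5.2.6 does not list it at the last integrative session. The Visit 13-to-6-month QoL-Q change in SAP 8.10.2.1 therefore cannot be computed. Baseline to Visit 14 can.

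**The case against.** A reader might infer that a non-significant result will be reported as lasting benefit. The documents do not say so: SAP 8.10.2.1 attaches no reading to either outcome, SAP 2.0 calls the study exploratory, and SAP 6.0 and Protocol 12.1 disclaim power. The defect that can be documented is the absence of a margin or interpretation rule behind an analysis whose stated purpose is to determine durability.

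A reader might also infer that no 6-month effect will be reported at all. That is too broad. The by-group descriptive statistics, the plots and the protocol's effect-size commitments stand, and for eight secondary scales the protocol expressly reaches into follow-up. What remains is that none of this defines a 6-month LSAS contrast or gives it an interval.

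If the planned t-test is between arms and data are complete, its mean difference plus the baseline-to-Visit-13 difference equals the baseline-to-Visit-14 difference. The point estimate is then recoverable, but its CI is not, and the SAP does not say that the test is between arms.

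The strongest reply is that the added contrast is weak too. Its half-width of 0.86 to 1.36 visit SDs exceeds an assumed 0.8 SD effect, so a fully retained effect of that size would give a CI including zero in 54–78% of trials. Protocol 5.2.7 lets subjects resume psychiatric medication or change outside psychotherapy after Visit 13, and subjects who stop treatment complete the visit only where possible. These limits stand. They argue for reporting the result as an estimate, not for leaving it undefined. Nor is there a need to delete the planned analysis; adding to it is enough.

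**Conclusion.** The point holds in this form. The SAP does not carry the 6-month part of the primary objective into a defined MDMA-minus-placebo LSAS estimate, and the one 6-month test it specifies cannot establish durability.

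The size depends heavily on assumptions that the documents cannot settle. Complete loss of benefit would be missed in about 0–50% of trials within the MDMA arm and 6–78% between arms, over effects of 0.8 to 1.5 SD and correlations of 0.5 to 0.8. At the favourable end (1.5 SD, within arm) the test would nearly always detect complete loss. Half loss is missed more often throughout. Whichever effect size applies, a non-significant result is not evidence of maintenance, and the unstated choice between a within-arm and a between-arm test changes the miss rate greatly.

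The change should be made, because it aligns the SAP with its own objective using data already scheduled for blinded collection.

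**What to change.** In SAP 8.10.2.1:
- Add the between-arm difference in LSAS change from baseline to Visit 14, by the same method as the primary analysis, with Cohen's d and a 95% CI, and name it as the 6-month treatment-effect estimate.
- Keep the Visit 13-to-Visit-14 change as supportive, reported by arm with a 95% CI. State that its non-significance is not treated as evidence of durability.
- Do the same for the secondary scales rated at Visit 14. For QoL-Q, replace the Visit 13-to-6-month change with baseline to Visit 14.
- State that the 6-month estimate includes the effect of medication or psychotherapy changes allowed after Visit 13, and that it is an imprecise estimate and not proof of durability.

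The cost is a few sentences of SAP text. No new visits, data or subjects are needed.
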